be collected immediately before the actual end of PF-06863135 infusion. For subcutaneous administration, the 2-hour sample should be taken at 2 hours post-injection ±12 minutes; also for SC administration, with the exception of cytokine samples, 2 and 4 hr samples are not needed other than on Cycle 1 D1.

† Sampling times are related to the start of the infusion. All efforts will be made to obtain the pharmacokinetic (PK) samples at the exact nominal time relative to dosing. However, samples obtained within the window specified will be considered acceptable.

Footnotes for Schedule of Pharmacokinetic, Soluble Factors and Cytokine Activities A

1. **Cytokine evaluation in serum:** See Cytokine Assessments Section 7.5.4 for a full list of cytokine assessments. All samples will be analyzed centrally. All 0 hour samples will be collected prior to investigational product administration on days whereby investigational product is to be administered. If CRS is suspected, an adhoc cytokine sample will be collected(see Section 7.1.3 Laboratory Safety Assessments). Should the site require cytokine information for patient management, the site will have the option of collecting an additional sample for local analysis. If a sample for cytokine panel evaluation is due to be collected on the same day as the day a suspected CRS event occurs, then an ad hoc sample for central analysis is not required/collected. However, an ad hoc sample for local analysis may still be collected for patient management.
2. **Blood sample for PF-06863135 blood level:** Approximately 5 mL sample of whole blood (to provide approximately 2 mL of serum) will be collected at each time point for PK analysis of PF-06863135. After Cycle 8, pre- and post-dose PK samples will be collected only on every 4th cycle (Cycle 8, Cycle 12, Cycle 16, etc.). An additional PK sample should also be taken if CRS is suspected, and a PK sample is not already scheduled to be taken (eg. Cycle 3 onwards).

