| Samples for pomalidomide blood level (Parts 1D and 2D only) ⁵ | | | | | | X | | | | | X | | | X | | | | | | | | | | | |
| Samples for dexamethasone blood level (Parts 1E and 2E only) ⁶ | | X | | | | X | | | | | X | | | X | | | | | | | | | | | |

PF-06863135

C1071001

Final Protocol Amendment 9, 28 March 2023

| Visit Identifier | Up to 7 days prior to C0D1 | Treatment Period | | | | | | | | | | | | | | | | | | EOT | | | | | |
|---|----------------------------|------------------|---|---|---|----|-----------------------------|----------------|----------------|----|----|-----|--------------------------|--------------------------|---|--------------------------|---|--------------------------|--------------------------|-----|--------------------------|-----|--------------------------|----|--------------------------|
| | | Priming Cycle | | | | | Maintenance Dose | | | | | | | | | | | | | | | | | | |
| Study Day | | Cycle 0 (1 wk) | | | | | Cycle 1 (1 Cycle = 4 weeks) | | | | | | | Cycle 2 | | | | | Cycle 3 onwards | | | | | | |
| | | 1 | | 2 | | D1 | | D2 | | D8 | | D15 | | D22 | | D1 | | D8 | | D15 | | D22 | | D1 | |
| | | 0 | 2 | 4 | 8 | 24 | 0 | 2 [*] | 4 [*] | 8 | 24 | 0 | 2 [*] (IV only) | 4 [*] (IV only) | 0 | 2 [*] (IV only) | 0 | 2 [*] (IV only) | 4 [*] (IV only) | 0 | 2 [*] (IV only) | 0 | 2 [*] (IV only) | 0 | 2 [*] (IV only) |
| Soluble BCMA and other factors ⁴ | X | X | X | X | X | X | X | X | X | X | X | X | X | X | X | X | X | X | X | X | X | X | X | X | |

Abbreviations: Anti-drug antibodies = ADA; BCMA = B-cell maturation antigen; D = Day; EOT = end of treatment; neutralizing antibodies =Nab.

* For IV administration, the 2-hour sample should be taken immediately (up to 15 minutes before) before the end of PF-06863135 infusion; if the infusion is longer than 2 hours (or shorter if a 1 hour infusion is tested), the collection time of this sample should be adjusted accordingly for the sample to be collected immediately before the actual end of PF-06863135 infusion. For subcutaneous administration, the 2-hour sample should be taken at 2 hours post-injection ±12 minutes. For Part 2 IV administration lead-in cohort, C2D1 end of infusion sample will be taken at 1 hr immediately (up to 15 minutes) before the end of PF-06863135 infusion. Also for SC administration, 2 and 4 hr samples are not needed other than on Cycle 0 D1 and Cycle 1 D1.

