† Sampling times are related to the start of the infusion. All efforts will be made to obtain the pharmacokinetic (PK) samples at the exact nominal time relative to dosing. However, samples obtained within the window specified will be acceptable.

Activities in grayed out columns should only be done for PF-06863135 Q1W dosing schedule but skipped for Q2W dosing.

Footnotes for Schedule of Pharmacokinetic, Soluble Factors and Cytokine Activities B

- Cytokine evaluation in serum:** See Cytokine Assessments [Section 7.5.4](#) for a full list of cytokine assessments. All samples will be analyzed centrally. All 0 hour samples will be collected prior to investigational product administration on days whereby investigational product is to be administered. If CRS is suspected, an adhoc cytokine sample will be collected (see [Section 7.1.3](#) Laboratory Safety Assessments). Should the site require cytokine information for patient management, the site will have the option of collecting an additional sample for local analysis. If a sample for cytokine panel evaluation is due to be collected on the same day as the day a suspected CRS event occurs, then an ad hoc sample for central analysis is not required/collected. However, an ad hoc sample for local analysis may still be collected for patient management.

PF-06863135

C1071001

Final Protocol Amendment 9, 28 March 2023

| Visit Identifier | Up to 7 days prior to C0D1 | Treatment Period | | | | | | | | | | | | | | | | | | EOT | | | | | | |
|------------------|----------------------------|------------------|---|---|---|----|-----------------------------|----------------|----------------|---|----|---|-----------------------------|-----------------------------|-----|-----------------------------|----|-----------------------------|-----------------------------|-----|-----------------------------|---|-----------------------------|---|-----------------------------|--|
| | | Priming Cycle | | | | | Maintenance Dose | | | | | | | | | | | | | | | | | | | |
| Study Day | | Cycle 0 (1 wk) | | | | | Cycle 1 (1 Cycle = 4 weeks) | | | | | | | Cycle 2 | | | | | Cycle 3 onwards | | | | | | | |
| | | 1 | | | 2 | | D1 | | D2 | | D8 | | D15 | | D22 | | D1 | | D8 | | D15 | | D22 | | D1 | |
| | | 0 | 2 | 4 | 8 | 24 | 0 | 2 [*] | 4 [*] | 8 | 24 | 0 | 2 [*] (IV only) | 4 [*] (IV only) | 0 | 2 [*] (IV only) | 0 | 2 [*] (IV only) | 4 [*] (IV only) | 0 | 2 [*] (IV only) | 0 | 2 [*] (IV only) | 0 | 2 [*] (IV only) | |

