3.2. Dose Limiting Toxicity (DLT) Definition

Monitoring for DLTs will occur during Part 1. Severity of adverse events (AEs) will be graded according to National Cancer Institute Common Terminology Criteria for Adverse Events (CTCAE) version 4.03. The severity of cytokine release syndrome (CRS) will be assessed according to the grading described by Lee et al. (2014 and 2019,^{2,3} See [Appendix 5](#)). For the purpose of dose escalation, the DLT observation period will be up to the end of Cycle 1 in each patient. For those patients receiving a priming dose, Cycle 0 and Cycle 1 would be included in the DLT observation period. DLT evaluable patients will include patients that have experienced a DLT in the DLT observation period or. DLT evaluable patients will also include those who received all of their planned doses of PF-06863135 in the initial DLT observation period if Q2W dosing is being evaluated or at least all but one of their planned doses of PF-0686135 if Q1W dosing is being evaluated, provided a dose was not missed due to toxicity attributed to study drug. Safety information from any patients that do not meet DLT evaluable criteria could still be considered for overall dose escalation decisions although they would not factor into mTPI decision rules.

Any of the following adverse events observed within the DLT observation period considered related to PF-06863135 or PF-06863135 in combination with lenalidomide, pomalidomide, dexamethasone, will be classified as DLTs:

Hematological:

- Grade 4 neutropenia lasting >5 days. Except in lenalidomide combination cohort where it can be managed by dose reduction of lenalidomide in the next cycle.
- Febrile neutropenia (defined as an absolute neutrophil count [ANC] <1000/mm³ with a single temperature of >38.3°C [101°F], or a sustained temperature of ≥38°C [100.4°F] for more than one hour). If fever is determined to be a symptom of CRS confirmed by clinical course and cytokine levels and resolves in a manner consistent with CRS, this would no longer be considered a DLT, and the patient may resume treatment.
- Grade ≥3 neutropenia with infection.
- Grade 4 thrombocytopenia (unless the study entry baseline count was ≥25,000 and <50,000 to take into account bone marrow suppression due to multiple myeloma, in

PF-06863135

C1071001

Final Protocol Amendment 9, 28 March 2023

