5.9.4. Cytokine Release Syndrome

Symptoms associated with CRS vary greatly and may be difficult to distinguish from other conditions. The more common symptoms include fever, nausea, headache, tachycardia, hypotension, rash and shortness of breath. The severity of symptoms can be mild to life threatening and thus there should be a high suspicion for CRS if these symptoms occur. If CRS is suspected, cytokines will be analyzed at central laboratories to determine if cytokine elevation consistent with CRS is observed (see [Section 7.1.3](#)). The severity of cytokine release syndrome (CRS) will be assessed according to the modified grading described by Lee et al. in 2014² as well as the more recent consensus grading from the American Society for Transplantation and Cellular Therapy (ASTCT)³ but only ASTCT will be used for management of CRS^{38,39} ([Appendix 5](#)).

For CRS DLT criteria, please see [Section 3.2](#).

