7.1.3. Laboratory Safety Assessment

Hematology, blood chemistry, viral, coagulation and pregnancy assessments will be drawn at the time points described in the **SCHEDULE OF ACTIVITIES** and analyzed at local laboratories. If CRS is suspected, an ad hoc cytokine sample will be collected and evaluated centrally (See **Section 7.5.4**). Should the site require cytokine information for patient management, the site will have the option of collecting an additional sample for local analysis. If a sample for pharmacodynamic cytokine panel evaluation is due to be collected on the same day as a suspected CRS event occurs, then an ad hoc sample for central analysis is not required/collected. However, an ad hoc sample for local analysis may still be collected for patient management. Local cytokine analysis may include interleukin (IL)-6, IL-1 β , tumor necrosis factor -alpha (TNF α), and/or IL-10 or other cytokines that will help the investigator with patient management.

If TLS is suspected, a sub-set of chemistry tests will be completed (ie, total calcium, creatinine, phosphorus or phosphate, potassium and uric acid) to confirm diagnosis if the tests were not performed within the last 24 hrs.

Table 11. Safety Laboratory Tests

| Hematology | Chemistry | Viral | Coagulation | Urinalysis | Pregnancy Test | Ad hoc Central Lab Cytokine Analysis [†] |
|----------------------|--------------------|---|-------------|---|---|--|
| Hemoglobin | ALT | HBsAg and HBcAb) with reflexive DNA testing | PT or INR | Urine dipstick for urine protein: If positive, collect 24-hr and microscopic (Reflex Testing) | For female patients of childbearing potential, serum. | IL-6, IL-10, IL-2, sIL2R, IL-12, IL-4, IL-5, IL-13, IL-17, IL-1b, IL-8, IFN γ , and TNF- α |
| Platelets | AST | HCV antibody with reflexive RNA testing | PTT | | | |
| WBC | bicarbonate | | | | | |
| Absolute Neutrophils | CRP | | | | | |
| Absolute Lymphocytes | Alk Phos | | | | | |
| Absolute Monocytes | Sodium | | | | | |
| Absolute Eosinophils | Potassium | | | | | Optional Ad hoc Local Lab Cytokine Analysis [†] |
| Absolute Basophils | Magnesium | | | | | |
| | Chloride | | | | | IL-6 |
| | Total calcium | | | | | IL-1 β |
| | Total bilirubin*** | | | | | IL-10 |
| | Total Protein | | | | | TNF α |
| | BUN or Urea | | | | | Other cytokines |
| | Creatinine | | | | | |

PF-06863135
 C1071001
Final Protocol Amendment 9, 28 March 2023

Table 11. Safety Laboratory Tests

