7.5.4. Cytokine Assessments

Samples will be collected for central evaluation of cytokines at the time points specified in the [SCHEDULE OF ACTIVITIES](#) and [Section 7.1.3](#). Instructions for sample collection,

PF-06863135

C1071001

Final Protocol Amendment 9, 28 March 2023

processing, storage and shipment will be provided in the study manual. All samples will be analyzed centrally. If CRS is suspected and coincides with a day pharmacodynamic samples are not collected per the [Schedule of Activities](#), an ad hoc cytokine sample should be collected (see [Section 7.1.3 Laboratory Safety Assessments](#)). In addition, should the site require cytokine information for patient management, the site will have the option of collecting an additional sample for local analysis.

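### In Schedule B with SC dosing, a pre-dose cytokine sample cancels the extra central sample for CRS suspected later that day, leaving no post-onset central value for that day

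*Protocol*

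**What the plan says.** Three sets of provisions meet here.

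**The waiver.** The cytokine footnote of Schedule B says, of a scheduled panel sample: "collected on the same day as the day a suspected CRS event occurs, then an ad hoc sample for central analysis is not required/collected". In short, the ad hoc central sample is dropped. Section 7.1.3 repeats this: "then an ad hoc sample for central analysis is not required/collected". Section 7.5.4 states the converse, with the ad hoc sample taken "If CRS is suspected and coincides with a day pharmacodynamic samples are not collected"; the note under Table 11 agrees. None of these asks whether the scheduled draw comes before or after onset.

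**The sampling times.** The Schedule B footnote fixes the zero-hour draw: "All 0 hour samples will be collected prior to investigational product administration on days whereby investigational product is to be administered". The asterisk note to that table adds: "Also for SC administration, 2 and 4 hr samples are not needed other than on Cycle 0 D1 and Cycle 1 D1".

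**The use of the result.** Section 5.9.4 gives the purpose of the central assay: "If CRS is suspected, cytokines will be analyzed at central laboratories to determine if cytokine elevation consistent with CRS is observed". Section 3.2 lets febrile neutropenia cease to be a DLT under a condition that begins "If fever is determined to be a symptom of CRS confirmed by clinical course and cytokine levels" and also requires resolution in keeping with CRS.

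A local sample stays available. The Schedule B footnote and Section 7.1.3 make it optional, for patient management. Appendix 5 is firmer and asks for a local sample in any suspected case, provided the draw does not interfere with treatment.

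**The concern.** A sample drawn before the dose, and so before a reaction to that dose, cannot show the cytokine rise the reaction causes. On later SC dosing days in Schedule B, that sample is the only one scheduled, and its presence on the calendar removes the one that could have shown the rise. Followed exactly, the rule gives less central information about CRS on a sampling day than on a day with no sampling at all.

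At stake is the evidence behind one DLT judgment. If a neutropenic patient develops fever on such a day, the exemption calls for cytokine levels as well as clinical course. Without a post-onset value, a CRS fever might be counted as a DLT, or a true DLT might be excused without the evidence that Section 3.2 requires. Schedule B matters because Section 3.4 adopts priming for both monotherapy and combination therapy.

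**Working it through.** The plan states no figure on this point, so there is none to reproduce. The check sets the provisions side by side and counts.

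1. Scheduled central cytokine samples in Schedule B, SC dosing:

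| Dosing day | Scheduled draws | Draws after the injection |
|---|---|---|
| C0D1 | 0, 2, 4, 8 h; 24 h on Day 2 | 3 that day, 1 the next |
| C1D1 | 0, 2, 4, 8 h; 24 h on Day 2 | 3 that day, 1 the next |
| C1D8, C1D15, C1D22 | 0 h | 0 |
| Cycle 2 dosing days | 0 h | 0 |

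   The later 2 h and 4 h columns are headed for IV only, and the asterisk note says the same for SC. The two agree, so the reading does not depend on the table layout.

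2. For CRS starting after the injection on C1D8, C1D15 or C1D22, post-onset central samples that day = 0 scheduled + 0 ad hoc (waived) = 0.

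3. Share of the DLT window. Section 3.2 includes Cycles 0 and 1 for primed patients. With weekly dosing the dosing days are C0D1, C1D1, C1D8, C1D15 and C1D22, so 3 of 5 have only a pre-dose sample. With Q2W dosing, omitting Days 8 and 22, they are C0D1, C1D1 and C1D15, so 1 of 3. These are shares of dosing days, not of CRS events.

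4. The other schedules. The corresponding note in Schedule A makes an exception: "also for SC administration, with the exception of cytokine samples, 2 and 4 hr samples are not needed other than on Cycle 1 D1". SC patients there keep post-dose cytokine draws. In Schedule C the cytokine row is not marked IV only, so they apparently do there as well. In both, the gap shrinks to onset after the last scheduled draw of the day. The full gap is specific to Schedule B, which lacks the exception.

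5. Where cytokine levels enter the DLT definition. They appear only in the febrile-neutropenia exemption. The Grade 3 and Grade 4 CRS criteria in Section 3.2 do not use them. An affected DLT judgment therefore needs all of: febrile neutropenia as defined there; CRS first suspected on one of these days after the pre-dose draw; no local sample; and no ad hoc central sample on a later non-sampling day while CRS is still suspected.

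6. What one reclassified event could do. In Table 4, moving from 0 to 1 DLT changes escalate to stay at n = 2, 3 and 4. At n = 5 to 12 both counts read escalate. Moving from 1 to 2 DLTs changes escalate to stay at n = 5 to 11.

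**The case against.** The strongest reply is that the gap is real on paper but small in effect. Section 3.2 does not require the cytokine levels to be central. A same-day local sample is expressly kept; Section 7.1.3 names IL-6, IL-1β, TNFα and IL-10 among the local options, and Appendix 5 says it should be supplied. If CRS is first suspected, or still suspected, on the next non-sampling day, Section 7.5.4 calls for the ad hoc central sample. Section 5.9.4 refers the reader to Section 7.1.3, which contains the waiver, so the two can be read as a general statement and its specific rule. Enrollment is complete (Section 3.1) and the monotherapy RP2D is chosen (Section 3.4), so rewording cannot change a past escalation decision.

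All of that stands as a limit on size. It does not close the gap: the local sample is optional in two places and expected in a third, and the central assay is the one given the confirming role. The relation to Section 5.9.4 is best described as a rule that defeats the stated purpose, not as a flat contradiction.

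Three stronger readings are tempting and not supported:

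- That a CRS fever on these days can never be confirmed, so DLT counts are wrong. A local result could serve, and the documents report no case where one was missing.
- That most patients are affected because CRS occurred in 87.8% of 41 (Section 1.2.3.1). That figure covers CRS at any time, QW or Q2W, with or without priming or premedication; it is not a rate for Days 8, 15 or 22.
- That the cytokine endpoint or the CRS analysis is compromised. The endpoint is pre- and post-dose quantification, and SAP Section 8.2.4 analyzes symptoms, onset, tocilizumab use and resolution. No planned analysis treats a pre-dose value as the CRS value.

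**Conclusion.** The point holds for Schedule B with SC dosing. On C1D8, C1D15, C1D22 and Cycle 2 dosing days, CRS that begins after the injection has no post-onset central cytokine value for that day. Schedule A, and apparently Schedule C, share the flaw only for onset after the last scheduled draw.

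The size is 3 of 5 dosing days in the weekly primed DLT window, and one of the DLT criteria. The number of patients affected cannot be derived from the documents. The conclusion assumes that sites follow the waiver as written and that the gap is judged by calendar day.

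With enrollment complete, the consequence for DLT decisions is mainly retrospective: it concerns what evidence supported any febrile-neutropenia exemption already granted. That makes this a worthwhile, inexpensive correction, not a finding that the MTD/MAD or RP2D is unsound.

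**What to change.** Reword the waiver so that the ad hoc central sample is omitted only when a scheduled cytokine sample will still be drawn after symptom onset on the same day. Make the change in the cytokine footnotes of Schedules A, B and C, in Section 7.1.3, in the note under Table 11 and in Section 7.5.4. These places should also agree on the trigger, since Section 7.5.4 and the Table 11 note refer to pharmacodynamic samples generally while the footnotes and Section 7.1.3 refer to the cytokine panel. Reconcile them with Section 5.9.4 and Appendix 5, and settle whether the local sample is optional or expected.

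In the clinical study report, for any febrile neutropenia exempted as CRS on one of these days, state which post-onset cytokine evidence supported the exemption, central or local, or that there was none.

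The cost is the wording change, a short case review, and one extra tube per affected event, the same draw already required on days without a scheduled sample.

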1. INTRODUCTION

1.1. Mechanism of Action/Indication

PF-06863135 is a bispecific monoclonal antibody against B-cell maturation antigen (BCMA, also known as tumor necrosis factor receptor superfamily member 17 [TNFRSF17] or cluster of differentiation [CD] 269) and CD3. Targeted T-cell mediated cytotoxicity follows the binding of one epitope of PF-06863135 to CD3 expressing T-cells, and a second epitope to BCMA expressing multiple myeloma cells. In this clinical study, PF-06863135 will be evaluated for the treatment of adult patients with relapsed or refractory multiple myeloma as monotherapy and in combination with lenalidomide, pomalidomide, or dexamethasone.

1.2. Background and Rationale

1.2.1. Multiple Myeloma

Multiple myeloma (MM) is a hematological malignancy that is characterized by uncontrolled expansion of bone marrow plasma cells. Approximately 114,000 new cases of MM are diagnosed worldwide each year, and 80,000 patients will die from their disease.⁶ In the US, the incidence of MM has increased from 4.91 per 100,000 in 1975, to 6.79 per 100,000 in 2013.⁷ More patients are diagnosed at an older age; 34.4 per 100,000 diagnosed at age 65 and over, whilst 2.4 per 100,000 are diagnosed under the age of 65.

MM is a disease that evolves from a pre-malignant stage of monoclonal gammopathy of undetermined clinical significance (MGUS), to asymptomatic smoldering myeloma, to symptomatic active myeloma.⁸ During the active stage of disease, a majority of patients develop painful bone lesions and organ dysfunction, leading to anemia, renal insufficiency and hypercalcemia. Whilst patients with smoldering myeloma do not require primary therapy, the treatment regimen for patients with active disease is currently dependent on the patient's eligibility to receive an autologous stem cell transplant (ASCT). For patients <70 years old with no comorbidities, induction therapy (either proteasome inhibitor-based or immunomodulation-based regimens) combined with an ASCT is the suggested approach, with 2-year survival achieved in 80% of patients.^{8,9} Still, even in this younger age group, the rate of toxicity following transplant is high, with 5% mortality due to adverse events reported in clinical studies.¹⁰ In older patients ie, those >70 years, adverse event related mortalities following ASCT is a staggering 19%.¹⁰ Though in theory allogeneic stem cell transplant has a curative potential, it is not a recommended regimen for this population as no survival advantages have been demonstrated in randomized studies due to increased toxicities.¹¹ For transplant ineligible patients, immunomodulation based regimen of bortezomib, lenalidomide, and dexamethasone is the primary preferred treatment option as it was demonstrated in the Phase III Southwest Oncology Group (SWOG) S0777 study that an objective response rate (ORR), of 71%, and progression free survival of 43 months can be achieved.^{9,12} However, toxicity remains to be a concern, with Grade 3 or higher neuropathy reported in 24% of patients.

PF-06863135

C1071001

Final Protocol Amendment 9, 28 March 2023

Despite a number of recent advances, the majority of patients are expected to relapse, even for those who respond initially to treatment. Even for patients who are eligible to receive autologous stem cell transplants, the median time to relapse was 17.2 months.¹³ Similarly, for patients that are treated with novel proteasome inhibitor-based or immunomodulation-based combination regimens as front line treatment, the median time to relapse is 16.4 months.¹⁴

Patients with relapsed refractory multiple myeloma who respond poorly to proteasome inhibitor-based or immunomodulation-based regimens show a median overall survival of only 1.5 years.¹⁵ In this relapsed setting, approximately 50% treatment-related adverse events (AE) and 20% serious adverse events (SAE) have been reported.¹⁶ Furthermore, each subsequent line of therapy renders the patient more refractory to treatment. For example, patients who are double-refractory to proteasome inhibitor-based or immunomodulation regimens have a median overall survival of 9 and 5 months.¹⁷ It is therefore clear that additional treatment approaches are required for relapsed/ refractory MM.

